**Table 9 List of Prohibited Medications and Non-Drug Therapies**

Medication	Examples
Use of anticoagulants	e.g. warfarin
Use of systemic immunosuppressants/immunomodulators	e.g. ciclosporin A, dapsone, methotrexate, mycophenolate, chloroquine, and comparable drugs
Use of oral, depot, or topical corticosteroids	e.g. prednisolone
Use of topical calcinurin inhibitors	e.g. tacrolimus, pimecrolimus
Use of tricyclic antidepressants with antihistaminergic properties	e.g. doxepin
Use of UV therapy	including PUVA.
Use of Ketotifen,	
Use of H2 antihistamines	e.g. ranitidine, cimetadine
Use of Leukotriene antagonists	e.g. montelukast
Part A and Part B only: Use of H1 antihistamines	e.g. cetirizine, loratadine
Part C Use of H1 antihistamines above the licensed dose	e.g. cetirizine, loratadine

## 6. STUDY ASSESSMENTS AND PROCEDURES

This section lists the procedures and parameters of each planned study assessment. The exact timing of each assessment is listed in the Time and Events Table Section [6.1](#). Whenever vital signs, 12-lead ECGs and blood draws are scheduled for the same nominal time, the assessments should occur in the following order: 12-lead ECG, vital signs, blood draws. The timing of the assessments should allow the blood draw to occur at the exact nominal time.

The timing and number of planned study assessments, including safety, pharmacokinetic, pharmacodynamic/biomarker assessments may be altered during the course of the study based on newly available data (e.g. to obtain data closer to the time of peak plasma concentrations) to ensure appropriate monitoring. The change in timing or addition of time points for any planned study assessments must be documented in a Note to File which is approved by the relevant GSK study team member and then archived in the study sponsor and site study files, but this will not constitute a protocol amendment. The IRB/IEC will be informed of any safety issues that require alteration of the safety monitoring scheme or amendment of the Informed Consent Form. No more than 500 mL of blood will be collected over the duration of the study, including any extra assessments that may be required.

Photographs may be taken of some of the procedures, tests, medical conditions or reactions which may occur during the study.

## 6.1. Time and Events Table

### 6.1.1. Part A: Healthy Volunteer Time and Event Table Dose group 1

Day:	Screening	-1	1	2	3	4	Follow-up	Notes
Visit Window (relative to Day 1)	-28 to -7						Day 5 to Day 7	
Admission to Unit		X						
Informed Consent	X							
Demographics	X							
Complete physical	X						X	
Body weight (kg)	X							
Height (cm) without shoes	X							
Brief physical		X						
Medical/medication/drug/alcohol history	X							
12-lead ECG 	X	X				X	X	1. Triplicate ECG at screening and CV risk factors questionnaire
Vital signs	X	X	X	X	X	X	X	
Urine drug/alcohol screen	X	X						
HIV, Hep B and Hep C screen	X							
Clinical Laboratory Tests	X	X				X	X	
Allergen Challenge-Skin Prick Test	X 		X 		X 	X 		2. SPT- Skin Prick Test analysis will be performed at ~15-20mins post challenge. 3. SPT with all 4 specified allergens 4. SPT using one allergen will be performed 6 hours post dose (see Section 6.4.1) 5. SPT using one allergen will be performed 24 hrs after the last dose
TSH 	X							6. TSH test only at screening only
Randomisation		X						

Day:	Screening	-1	1	2	3	4	Follow-up	Notes
Visit Window (relative to Day 1)	-28 to -7						Day 5 to Day 7	
Tolerability Assessment			X  ←-----→					7. Tolerability assessment at pre – and ~6 hours post-dose
AE assessment		X	←-----→				X	
Concomitant Medication		X	←-----→				X	
Pharmacokinetic Blood Sample 			X	X	X	X 		8.PK blood sample taken at pre dose, 1,2, 4, 8, 12 and 24hr post dose 9.PK refers to sample 24 hours post dose
Study Treatment Dosing			X	X	X			
Discharge from unit						X		
Outpatient visit	X						X	

### 6.1.2. Part A: Healthy Volunteer Time and Event Table Dose group 2

Day:	Screening	-1	1	2	3	4	5	6	7	8	Follow-up	Notes
Visit Window (relative to Day 1)	-28 to -7										Day 9 – Day 11	
Admission to Unit		X										
Informed Consent	X											
Demographics	X											
Complete physical	X										X	
Body weight (kg)	X											
Height (cm) without shoes	X											
Brief physical		X										
Medical/medication/drug /alcohol history	X											
12-lead ECG 	X	X								X	X	1. Triplicate ECG at screening and CV risk factors
Vital signs	X	X	X	X	X	X	X	X	X	X		
Urine drug/alcohol screen	X	X										
Urine for metabolite analysis			X 			X 						10. Pre dose and pool samples taken 0-12 and 12-24 hours post dose 22. Pool samples taken 0-12 and 12-24 hours post
HIV, Hep B and Hep C screen	X											
Clinical Laboratory Tests	X 	X 		X 		X 	X 		X 	X 		9. Pre-dose AST, ALT, Alkaline Phosphatase, Total Bilirubin Only- : results to be communicated to the GSK Medical monitor on the same day 17.Clinical lab test as per Section 6.3.4 of the protocol

Day:	Screening	-1	1	2	3	4	5	6	7	8	Follow-up	Notes
Visit Window (relative to Day 1)	-28 to -7										Day 9 – Day 11	
Allergen Challenge- Skin Prick Test	X 		X 		X 	X 		X 				3. SPT- Skin Prick Test measurements will be performed ~15-20 mins post challenge. 4. SPT with all 4 specified allergens 5. SPT will be performed 6 hours post dose 7. SPT will be performed 48 hours post dose of Day 4 (on the morning of Day 6)
TSH 	X											2. TSH test only at screening only
Randomisation		X										
Tolerability Assessment			X  ←-----→ only on dosing days 1 to 4									11. Tolerability assessment at pre – and ~6 hours post-dose on dosing days
AE assessment		X	←-----→							X		
Concomitant Medication		X	←-----→							X		
Pharmacokinetic Blood Sample			X 	X 	X 	X 	X 	X 	X 	X 		6. PK blood sample taken at pre dose, 1, 2, 4, 8, 12 and 24hours post previous dose 18. PK blood sample taken at 30, 36, 48 hours, post dose of Day 4 19. PK blood sample taken at 54, 60, 72 hours, post dose of Day 4 20. PK blood sample taken at 78, 84 hours post dose of Day 4 21. PK blood sample taken at 96 hours post dose of Day 4

Day:	Screening	-1	1	2	3	4	5	6	7	8	Follow-up	Notes
Visit Window (relative to Day 1)	-28 to -7										Day 9 – Day 11	
Blood Sample for CD69 expression			X 			X 	X 		X 	X 		12. Predose 13. 4 hours post dose of Day 4 14. 24 hours post dose of Day 4 (sample taken in the morning of day 5) 15. 72 hours post dose of Day 4 16. 96 hours post dose of Day 4
Study Treatment Dosing 			X	X	X	X						8. This will be once daily dosing using fresh bottles at 1% strength in the morning
Discharge from unit											X	
Outpatient visit	X										X	

### 6.1.3. Part B: Cold urticaria Subjects Time and Event table

Day:	Screening	-1	1	2	3	4	Day 6 to 15	Follow-up (Day 17-19)	Notes
Visit Window (relative to Day 1)	-28 to -7 days 								1. Screening can occur on any day between 28 days and 7 days prior to Day 1 dosing.
Admission to Unit		X							
Informed Consent	X								
Demographics	X								
Complete physical	X							X	
Body weight (kg)	X								
Height (cm) without shoes	X								
Brief physical		X							
Medical/medication/drug/alcohol history	X								
12-lead ECG	X 	X			X			X	2. Triplicate ECG at screening and CV risk factors
Vital signs 	X	X	X	X	X		X	X	3. Should be performed at the same time points as PK samples are taken
Urine drug/alcohol screen	X	X							
Pregnancy Test (women) 	X(S)		X(S/U)			X (S)	X(S)		4. Pregnancy test will be performed 3 times during screening, serum on day -28, day -7 to -4, and a serum or urine pregnancy test the day of the start of the study prior to dosing and a serum pregnancy test between day 10-12 (to coincide with a PK sample) and at the follow up visit.
HIV, Hep B and Hep C screen	X								
Clinical Laboratory Tests	X	X			X			X	

Day:	Screening	-1	1	2	3	4	Day 6 to 15	Follow-up (Day 17-19)	Notes
Allergen Challenge-SPT	X 		X 		X 	X 			5. SPT- Skin Prick Test measurements will be performed ~15-20mins post challenge 6. SPT using all 4 specified allergens 7. SPT will be performed at 6 hours post dose (see Section 6.4.1), and at 24 hours post last dose on day 3 8. SPT will be performed pre-dose on Day 1
TSH, free T4, T4, T3	X					X	X 	X	9. One sample between day 10-12 to coincide with PK sample
Cold Temp Test (Temp Test 4.0)	X		X 		X 	X 			10. Pre-dose 11. 6 hours post dose 12. 24 hours post last dose on Day 3
Randomisation		X							
Tolerability Assessment			←-----X  -----→						13. Tolerability assessment at pre – and ~6 hours post-dose
AE assessment			←-----X-----→				X		
Concomitant Medication		X	←-----X-----→				X		
Pharmacokinetic Blood Sample			X 	X 	X 	X 	X 	X	14. PK blood sample taken at pre dose, 1, 4, 8, 12hr post dose 15. One PK sample to be taken 24 hours post last dose on Day 3 16. One PK blood sample per day will be taken as follows: PK samples will be obtained on the following days (± 1 day): Day 6, 9, 12, & 15.
Study Treatment Dosing			X	X	X				
Discharge from unit					X				
Outpatient visit	X					X	X		
Blood Sample for CD69 expression			X 		X 		X 	X 	17. Pre-dose 18. 4 hrs post-dose 19. Sample collection should coincide with PK sample collection.

### 6.1.4. Part C: Chronic Spontaneous Urticaria Cohort

Day:	Screening	1	2	3	4	5	6	7	8	Day 10 ( $\pm$ 1 day)	Day 15 ( $\pm$ 1 day)	Follow-up Day 22 ( $\pm$ 1 day)	Notes
Visit Window (relative to Day 1)	-28 to -7 												1. Screening can occur on any day between 28 days and 7 days prior to Day 1 dosing.
Informed Consent	X												
Demographics	X												
Complete physical	X											X	
Body weight (kg)	X												
Height (cm) without shoes	X												
Brief physical		X											
Medical/medication/drug/alcohol history	X												
12-lead ECG	X 	X						X				X	2. Triplicate ECG at screening and CV risk factors
Vital signs	X	X		X			X			X 	X 	X 	3. To be performed on same day as PK samples
Urine alcohol screen	X	X											
Pregnancy Test (Women of child bearing potential) 	X(S) 	X (U) 						X(U) 		X (S)	X(S)		4. A serum (S) pregnancy test will be performed on the day of screening. If the day of screening is between Days -13 and -7, a further pregnancy test will not be required until Day 1. However, if the day of screening is between Days -28 and -14, an additional serum pregnancy test will be required between Days -7 and -4.

Day:	Screening	1	2	3	4	5	6	7	8	Day 10 ( $\pm$ 1 day)	Day 15 ( $\pm$ 1 day)	Follow-up Day 22 ( $\pm$ 1 day)	Notes
													5. A urine pregnancy test is required prior to dosing on Day 1 & Day 7
HIV, Hep B and Hep C screen	X												
Clinical Laboratory Tests	X	X						X				X	
TSH, free T4, T4, T3	X							X		X6	X6	X6	6. Sample to be taken on same day as PK sample
Blood Sample for CD69 expression		X 		X 		X 			X 	X 	X 		7. Pre-dose 8. 4 hours post dose 9. Sample to be taken on same day as PK sample
Randomisation		X											
UAS-7 Diary	X 		X 	X					10. Screening UAS7 diary will be completed for the 7 successive days before Randomisation (Day 1). If there is a lapse in any day prior to Day 1 the subject must complete the full 7 days worth of diary entries again during the screening period. 11. The UAS-7 diary should be completed pre-dose on those days where dosing occurs				
QOL (DLQI)	X	X 							X				12. The baseline DLQI assessment on Day 1, looking back over the previous 7 days prior to dosing, should be completed pre-dose

Day:	Screening	1	2	3	4	5	6	7	8	Day 10 ( $\pm$ 1 day)	Day 15 ( $\pm$ 1 day)	Follow-up Day 22 ( $\pm$ 1 day)	Notes
AAS	X 		X 	X				13. Screening AAS will be completed for the 7 successive days before Randomisation (Day 1) (on the same days as the UAS7). If there is a lapse in any day prior to Day 1 the subject must complete the full 7 days worth of diary entries again during the screening period. 14. The AAS assessment should be completed pre-dose on those days where dosing occurs					
AE assessment		←		X	→							x	
Tolerability Assessment at pre-dose		X 		X 		X 							15. Tolerability assessment at 1 to 2 hours post-dose
BHR- Basophil Histamine Release Test		X 											16. Two samples to be taken pre-dose
Pharmacokinetic Blood Sample		X 		X 		X 			X 	X 	X 		17. PK blood sample taken at pre-dose and 4hr post dose 18. Sample to be taken on same day as CD69 sample, TSH, free T4, T4, T3 samples and vital signs
Study Treatment Dosing		X		X		X							
Con Meds		←		X	→							x	
Outpatient visit	X	X		X		X		X	x	X	X		

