## Revision Chronology

GlaxoSmithKline Document Number	Date	Version
2013N167482_00	2014-APR-16	Original
2013N167482_01	2014-SEP-05	Amendment No. 1
Reason for Amendment 01:		

Changes have been made to safety related study specific dose adjustment criteria following MHRA review.
 
An update has been made to the exclusion criteria of the protocol Section 4.2.2. and a change has been made to Section 10.2 Regulatory and Ethical considerations following German (Berlin) Ethics Committee review.
		
2013N167482_02	2014-DEC-10	Amendment No. 2
Reason for amendment 02:		

Changes have been made to list all of the challenge agents to be used in the study following guidance from German Regulatory Agency (BfArM).
 
A table of the list of challenge agents has been added to the study treatment section. An update to the skin prick test procedure and the correct name of one of the challenge agents has been added to the inclusion criteria.
		
2013N167482_03	2015-JUN-07	Amendment No. 3

Part B and C have changed from a bilateral to a placebo-controlled randomised parallel design 3:1 active to placebo.
 
An informal review of data from the first 4 patients of Part B will be performed before starting part C
 
The number of subjects in Part C has increased (from n=12 up to n=16); and a 2-week PK, safety and biomarker endpoints sampling period for parts B & C has been implemented
		
2013N167482_04	2016-APR-11	Amendment No. 4

Updates have been made following the interim analysis of the first 4 subjects in Part B, related to the dosing in Parts B and C.
 
A change has been made to the inclusion and exclusion criteria, related to use of contraception for women of child bearing potential.
		

Changes have been made to the PK sampling time points for Part C.		
2013N167482_05	2016-OCT-13	Amendment No. 5
Administrative amendment to account for the change in primary medical monitor, as documented in the Medical Monitor and Sponsor Contact Information table.		
In addition, the following corrections have been made that were previously captured in a note to file format. The following file note is hereby superseded:		

• File note dated 26th April, 2016 concerning two clarifications of typographic/edits errors: Timing of tolerability assessment, and timing of the complete physical exam. These have been updated in Section 6.1.4

		

2013N167482\_05

CONFIDENTIAL

200196

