#### **4.2.1.4. Additional Inclusion criteria specific for subjects with chronic spontaneous urticaria (Part C)**

Subjects will be included in the chronic spontaneous urticaria cohort if all the following criteria apply

1. The subject is aged between 18 and 70 years of age inclusive, at the time of signing the informed consent.
2. Body weight  $\geq$  50 kg and BMI within the range 19 to 35 kg/m^2 (inclusive)
3. Subjects who have a score of  $>14$  on the UAS7 questionnaire with between 4-20 weals observed in a defined area of the body will be included in this study. This area must include either arms, legs or torso for 7 consecutive days during the screening period, prior to the Day 1 visit. If a subject has not completed 7 consecutive days of UAS questionnaire prior to dosing on Day 1 due to exceptional circumstances, the screening period may be extended until the subject has completed 7 consecutive days of UAS questionnaire. This will only be at the discretion of the Investigator.
4. No other aetiology identified for chronic urticaria such as drug-related or inducible urticaria as determined by history, physical examination and laboratory studies.
5. Subjects must be free from any past or present benign or malignant skin conditions and disease, other than the specified condition required for eligibility of subjects as defined in the specific inclusion criteria for CsU cohort unless in the opinion of the investigator it will not compromise the subjects safety and quality of data.

6. Other than a diagnosis of chronic spontaneous urticaria the subject should have no other co-morbidities which would introduce additional risk factors and will not interfere with the study procedures, as determined by a responsible and experienced physician, based on a medical evaluation including medical history, physical examination, laboratory tests and cardiac monitoring.
7. A subject with a clinical abnormality or laboratory parameter(s) which is/are not specifically listed in the inclusion or exclusion criteria, outside the reference range for the population being studied may be included only if the Investigator, in consultation with the GSK Medical monitor if required, agrees and documents that the finding is unlikely to introduce additional risk factors and will not interfere with the study procedures.

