### **5.5.1. Dose-Limiting Toxicity**

Toxicity is defined as dose-limiting toxicity if it meets the following criteria:

- Occurs within 6 hours after any dose for Parts A & B, or within 24 hours after any dose for Part C.
- and is considered by the Investigator to be possibly or probably related to treatment
- and, for AE or laboratory abnormality, is severe
- and, for tolerability,
  - is of Grade 3 or higher for “dermal response scoring (i)”, and
  - is Grade C, F, G, or H according to the “other effects scoring (ii)” (Section [6.3.4.1](#))

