AAS	X 		X 	X				13. Screening AAS will be completed for the 7 successive days before Randomisation (Day 1) (on the same days as the UAS7). If there is a lapse in any day prior to Day 1 the subject must complete the full 7 days worth of diary entries again during the screening period. 14. The AAS assessment should be completed pre-dose on those days where dosing occurs					
AE assessment		←-----X-----→								x			
Tolerability Assessment at pre-dose		X 		X 		X 							15. Tolerability assessment at pre-dose on each day
BHR- Basophil Histamine Release Test		X 											16. Two samples to be taken pre-dose
Pharmacokinetic Blood Sample		X 		X 		X 			X 	X 	X 		17. PK blood sample taken at pre-dose and 4hr post dose 18. Sample to be taken on same day as CD69 sample, TSH, free T4, T4, T3 samples and vital signs
Study Treatment Dosing		X		X		X							
Con Meds		←-----X-----→								x			
Outpatient visit	X	X		X		X		X	x	X	X		

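### The Part C tolerability row contradicts its own note on whether a pre-dose skin score exists, and the scheduled scores stop 22 to 23 h short of the end of the 24 h DLT window

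*Protocol*

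**What the plan says.** Protocol 2.1 lists local tolerability among the primary endpoints for Parts A, B and C. Section 6.3.4.1 defines the score: a dermal grade from 0 to 7 plus a letter for other effects.

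- **Part C, 6.1.4.** The row is labelled "Tolerability Assessment at pre-dose" and marked on the dosing days. Its note says "15. Tolerability assessment at 1 to 2 hours post-dose". The row has no later entry.
- **Part B, 6.1.3.** "13. Tolerability assessment at pre – and ~6 hours post-dose". Part A uses the same two times.
- **DLT window, 5.5.1.** "Occurs within 6 hours after any dose for Parts A & B, or within 24 hours after any dose for Part C".
- **Part C population, 4.2.1.4.** Subjects with a qualifying UAS7 score "with between 4-20 weals observed in a defined area of the body will be included in this study". That area has to include the arms, legs or torso. Section 3.1.5 has the cream spread over those same regions on Days 1, 4 and 7.
- **SAP.** The notes to Table 3 (7.1.1) restrict tolerability analyses to Parts A and B, and SAP 11.4.3 describes the scoring for those two parts only. The Part C schedule in SAP 11.2.1.4, taken from protocol amendment 2, has a third wording: pre-dose and post-dose, attached to the AE row.

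As history only, before Amendment 5 the note read "15. Tolerability assessment at pre-dose on each day". The Revision Chronology lists "Timing of tolerability assessment, and timing of the complete physical exam" among corrections of typographic or editing errors. The note changed and the row label did not.

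**The concern.** A site following 6.1.4 cannot tell whether to score the skin before applying cream. This matters more in Part C than elsewhere because weals are part of the disease and may lie under the cream. The dermal scale gives 4 for definite swelling and 5 for redness with swelling and papules, so a weal can score highly. Without a score from just before dosing, a high value at 1 to 2 h may be disease, irritation or both.

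The second issue is timing. In Parts A and B the post-dose score falls at the end of their 6 h DLT window. Part C has a window four times as long, in outpatients, and its only post-dose score comes earlier.

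The tolerability limb of the DLT definition is built on these scores. DLTs feed individual withdrawal (5.7.3) and the two-subject trigger for Safety Monitoring Committee discussion (5.6). Tolerability also informs the review of the first four Part C subjects (5.5.3.4).

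**Working it through.** The plan gives no figure to reproduce. The check is schedule arithmetic under each reading of the row.

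**Inputs.** DLT window: 6 h (A, B) and 24 h (C), from 5.5.1. Last scheduled post-dose score: about 6 h (A, B; 6.1.1 to 6.1.3) and 1 to 2 h (C; 6.1.4 note 15). Part C dosing on Days 1, 4 and 7, with n = 16 randomised 3:1, from 3.1.5.

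**1. Part of the DLT window after the last scheduled score** = window − score time.
- Parts A and B: 6 − 6 = about 0 h.
- Part C, scored at 2 h: 24 − 2 = 22 h; 22/24 = 91.7%.
- Part C, scored at 1 h: 24 − 1 = 23 h; 23/24 = 95.8%.

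This does not depend on how the row is read. Doses are 3 × 24 = 72 h apart, so a pre-dose score on Day 4 or Day 7 falls about 72 h after the previous dose, outside that dose's 24 h window. Nothing is scored after the Day 7 post-dose score.

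**2. Scores per subject.**

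| Reading | Scores per subject | Baseline score | Age of latest score at the Day 4 and Day 7 doses |
|---|---|---|---|
| Note 15 alone governs | 3 × 1 = 3 | none | 72 − 2 = 70 h to 72 − 1 = 71 h |
| Label and note both apply | 3 × 2 = 6 | yes, Day 1 | same-day pre-dose score |

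**3. Which reading applies.** The amendment history favours the first: the pre-dose note was replaced, not supplemented, and where the protocol wants both times (Parts A and B) it names both. But the label in force still says pre-dose. The SAP's copy of the schedule names both times, but rests on an older protocol and cannot settle the matter.

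**4. Size of the comparison arm.** 16 × 3/4 = 12 active and 16 × 1/4 = 4 placebo.

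**5. Can a weal alone be a DLT?** In 5.5.1 the tolerability limb requires dermal grade 3 or higher, and also a letter grade of C, F, G or H (peeling and cracking, fissures, serous exudate, or erosions and scabs), and investigator attribution as possibly or probably related. A weal graded 4 or 5 without one of those letter effects does not meet it.

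**The case against.** The strongest reply is that much of the apparent damage rests on one reading of the row, and that the score is not the only safety observation.

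- **A reader might infer that Part C certainly has no pre-dose score.** The text in force does not establish this, because the row label says the opposite. The missing baseline and the 70 to 71 h gap are conditional.
- **A reader might infer that weals will generate false DLTs.** Step 5 shows otherwise. Section 7.1.3 also requires the letter grade, together with a dermal score of 2 or above, before a skin score is reported as an AE.
- **A reader might infer that cream goes onto skin nobody has looked at.** Subjects attend before the Day 4 and Day 7 doses (3.1.5), and the investigator or designee applies the treatment under medical supervision (5.12). What may be missing is a recorded score.
- **A reader might infer that 22 to 23 h of the window is unobserved.** It is unscored. The 24 h defines when a toxicity occurs, not how often skin is scored. AEs are collected throughout, severe related AEs count as DLTs without a skin score, and 6.3 allows extra safety time points.
- **Other records bear on attribution.** There is a skin examination in the Day 1 brief physical, a UAS7 diary completed pre-dose on dosing days, and a randomised placebo arm in which disease should appear as noise rather than bias.

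All of this stands, but it gives only partial cover. The brief physical is scheduled only on Day 1, has no stated pre-dose time and yields no irritation score. The diary is patient-reported, and its weal questions in Appendix 3 ask for no body site. Placebo is four subjects. AE reporting excludes expected signs of the disease under study (7.1.3), so a reaction that resembles urticaria still needs a before-and-after comparison to be classified.

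**Conclusion.** Two points hold without any assumption. First, the row label and note 15 conflict on the timing of a primary safety endpoint. Second, no irritation score is scheduled in the last 22 to 23 h (92% to 96%) of the 24 h Part C DLT window, whereas Parts A and B have essentially no such gap.

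A third point holds only if note 15 overrides the label: three scores per subject, no baseline, and none before the second and third doses. Attribution of a high score in subjects with active weals would then be unreliable. It would not be impossible, given the partial cover above.

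The documents do not support claims that weals by themselves become DLTs, that skin goes unseen before re-dosing, or that the window is unobserved. I take no view on which DLT window or post-dose score time is right.

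**What to change.** 1. **Protocol 6.1.4.** Make the row label and note 15 agree: a score before cream is applied and the 1 to 2 h post-dose score, on Days 1, 4 and 7. Report post-dose change from that day's pre-dose score.
2. **SAP 7.1.1 and 11.4.3.** Bring Part C into the tolerability analyses and name the same-day pre-dose score as its baseline. SAP 11.4.3 limits the combined score to a maximum of 3. The SAP should say whether Part C change is taken before or after that limit, because a pre-dose weal graded 4 or 5 would already be at the ceiling.
3. **Protocol 5.5.1 and 6.1.4.** The 24 h DLT window and the skin-scoring times must be reconciled. Adding a score at the 4 h blood draw or at Day 10 would not do this: 24 − 4 = 20 h would still follow the 4 h score, and Day 10 is about 72 h after the last dose.

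**Cost.** Items 1 and 2 need wording changes and a few minutes of visual scoring per dosing day. Subjects are already in clinic for a pre-dose PK sample on each of those days, so no visit is added. Section 6 lets assessment timing be changed by a Note to File, but the table itself should be corrected so that label and note no longer disagree.
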